### 4. List of Planned Study Analyses

#### 4.1. Interim Analysis

No interim analysis is planned. Within Part B, when later-onset patients are completed then the final analysis will be performed on the later-onset patients. The unblinding plan details the steps to ensure that the blind is maintained throughout the entire study and for the infantile-onset patients should the later-onset patients be unblinded.

#### 4.2. Primary Analysis

N/A

#### 4.3. Final Analysis

The final analysis will be performed when all later-onset participants in Part B have completed the follow-up period.

# 4.4. General Principles

Descriptive summary statistics will be presented for all endpoints collected. Unless otherwise specified, for continuous endpoints, the summary statistics will generally include number of participants with data, mean, standard deviation, median, 25th percentile, 75th percentile, minimum and maximum. For categorical endpoints, the summary statistics will generally include number of participants with data, and the percentage of those with data in each category.

All summaries and listings will be presented by study groups unless otherwise specified. Visits in listings will be displayed as per CRF data collection rather than analysis visits.

The statistical software, SAS®(Version 9.4) will be used for all summaries and statistical analyses.

#### Visit Windows for Early Withdrawal, Unscheduled Visits

Data from early withdrawal visits and post baseline unscheduled assessments will be assigned to an appropriate scheduled post baseline visit using a windowing scheme for assessments that are tabulated or summarized by visit. Scheduled visits will not be windowed.

The visit windowing will be performed for efficacy and safety endpoints.

For safety endpoints the following windows will be utilized.

Visit	Lower Bound	Upper Bound	Target Day
Baseline			<=1
Day 15	2	21	
Day 29	22	47	29
Day 64	48	99	64

#### Table 2: Visit windows for safety Endpoints in 232SM203

Product: Nusinersen		Statistical Analysis Plan	
Study: 232SM203			Version: 1.0
Day 135	100	159	135
Day 183	160	232	183
Day 279	233	290	279
Day 302	291	348	302

For efficacy endpoints, the actual day of the unscheduled or end of study visits will be considered.

For post baseline visits up to and including Day 64 a +/-7 day window will be used and for visits between Day 135 and Day 302 a +/-14 day window will be used.

The following rules will be implemented for windowing:

- If more than one observation is within the same window, data from the regular scheduled visit will be used for that visit.
- If neither of the observations are from a regular scheduled visit the observation closest to the planned target date will be used. However, if both the observations are equidistant from the target date, the latest one will be used; if repeated measurements are on the same day, then the last measurement will be used.
- If windowing safety data safety data and there is more than one observation in a window for a dosing visit the observation on the day of dosing will be chosen over the observation where dosing did not occur on the same day.
- In windowing laboratory data, if a central and local result is available within the window then the central laboratory result will be chosen.

Study	Windowing
CS4	All dosed subjects will be included, and the Month 6 and Month 9 values collected will be utilized.
CS11	All dosed subjects meeting the re-evaluated conditions will be included. The protocol defined Day 265 visit will be used. If this was not collected since the subject moved to MMDR dosing, then Day 265 will be missing.
PMS study	The HFMSE visit data will be windowed to give Month 9 as study day 274 +/- 15 days. Therefore, study days between 259 and 289 will be considered, if >1 lie in the window the one closest to Day 274 will be selected. If two are equally close, the latest one will be selected.

#### Summary table of windowing for the external data

#### 4.5. Participant Accountability

The number (and percentage) of participants screened, screening failure, randomized, withdrew prior to dosing, dosed, completed treatment, discontinued treatment and the reasons for discontinuation from treatment, completed the study, withdrew from the study and reason for withdrawal will be summarized in a table.

A listing of participants who discontinued treatment/withdrew from study and the associated reasons for discontinuation/withdrawal will be presented. A separate listing will also be presented for participants who discontinued treatment/withdrew from study due to the COVID-19 pandemic or to humanitarian emergencies if applicable.

#### 4.6. Demographic and Baseline Characteristics

Baseline data (demography, medical history, SMA history, and baseline disease characteristics) will be summarized.

Formal statistical analyses will not be done to test for homogeneity between treatment groups. If there are apparent heterogeneities between the groups in any of the participant characteristics that are of clinical importance or could affect the treatment outcome, the impact of the imbalances will be investigated and, if appropriate, adjustments made in the efficacy and safety analyses.

Demography includes age at screening, age at first dose, sex, ethnicity, race, country and geographic region. Medical history will be coded in MedDRA and the number and percentage of participants with each medical history presented by preferred term.

SMA history includes age of symptom onset, time from disease onset to enrollment, age at SMA diagnosis, time from diagnosis to enrollment, number of copies of the SMN1 and SMN2 gene, highest motor function achieved and maintained, wheelchair use.

Baseline disease characteristics will be assessed by HFMSE, WHO motor milestones, Revised Upper Limb Module Test Total score and Entry item, growth parameters and Cobb angle. These assessments are further described in the next paragraph and Section 5.

Demographic and baseline disease characteristics will be presented for the ITT Set, the PPS and the Safety Set as appropriate.

#### 4.7. Protocol Deviations

Protocol deviations identified during site monitoring will be captured in a protocol deviation log and categorized as major or minor deviations. These deviations will be listed. Major protocol deviations will be summarized including those that lead to exclusion from the Per protocol Set.

Participants with incorrect stratification i.e. any mismatch between the stratification used for randomization on the IRT system and the actual stratification according to the eCRF will also be listed. A separate summary of major protocol deviations related to the COVID-19 pandemic will be presented.

### 4.8. Study Treatment Exposure

The number of doses received, and the number of sham procedures performed will be displayed using frequency distributions. The cumulative amount of nusinersen received will be summarized using summary statistics.

The overall time on study will be summarized descriptively by treatment. Overall time on study will be calculated (section 3.1). The duration will also be categorized and summarized using the following categories: <29 days, >=29 to 64 days, >=64 to 99 days, >=99 to 135 days, >=135 to 183 days, >=183 to 218 days, >=218 to <260, >=260 to 302 and >=302 days

Given the long half-life of nusinersen, participants are considered to be exposed from the time the first dose of nusinersen was administered (in or before the start of study) to the date of last visit or contact.

Separate listings will be provided showing what participants were randomized to as well as study drug administration data which will include lot numbers, actual treatment received, cumulative number of doses and cumulative doses. A listing of dosing errors will also be provided i.e. where either the incorrect dose was administered compared with the kit description from IRT system. A listing will also be presented to show whether any of the missed doses are related to COVID-19. If any of the doses are due to COVID-19, then the number of impacted doses will be presented.

#### 5. Efficacy Endpoints

#### 5.1. General Analysis Methods for Efficacy Endpoints

#### 5.1.1. Multiple imputation (MI)

In the event of missing data for post baseline visits then multiple imputation will be performed.

For secondary, second endpoints the multiple imputation method [Schafer 1997, Schafer 1999] will be used for patients who discontinue for a reason other than death or have a missing efficacy result at the timepoint of interest. This will be performed for HFMSE, RULM, NfL CSF and plasma concentration, ACEND, and PedsQL.

The imputations will be performed on total scores for post baseline visits. All available data will be used i.e., where participants have missed doses but continued to perform assessments; otherwise, any missing values will be imputed using MI.

If the MI procedure imputes any values outside the expected range for the scale e.g. from 0 to 66 for HFMS-E then values below 0 will be set to 0 and values above 66 will be set to be 66, and for NfL the minimum will be set to LLOQ/2.

The Markov Chain Monte Carlo (MCMC) method will be used to impute the missing score.

The treatment variable will be coded so that the Higher dose group is the first in the sort order. Prior to the Proc MI step the dataset will be sorted by treatment and then ascending unique subject identifier (USUBJID). The variable list in the model for imputations will include:

• treatment group, age at screening, baseline plasma NfL baseline value for the endpoint, and all available post baseline values

Product: Nusinersen	Statistical Analysis Plan
Study: 232SM203	Version: 1.0

A set of 100 complete imputed datasets will be generated and the relative efficiency parameter will also be checked to determine the acceptability of the imputed results i.e. it should be close to 98% or higher.

For each of the 100 imputed datasets, the endpoint will be compared between treatment groups using an ANCOVA model for continuous endpoints or logistic regression for binary endpoints as described in the main analysis for each endpoint.

The estimates from the 100 fitted models will be combined to provide an overall estimate with corresponding confidence intervals and p-value using PROC MIANALYZE [Little et al, 2002].

For the continuous endpoints, the difference between treatments and the corresponding CI will be presented. For the analyses using logistic regression the odds ratio and corresponding CI will be presented. In addition, the estimates of the binomial proportions in each treatment arm and the differences between treatments will be presented (Ratitch, 2013).

In the presentation of results from multiple imputed data, the number of subjects with missing data will be summarized.

For any given endpoint such as HFMSE, a number of different comparisons are planned such as within study 232SM203: 12mg to higher dose, sham versus higher dose, L3Q6 compared to higher dose. For each comparison a separate multiple imputation procedure will be performed including the 2 corresponding treatment groups. Only visits in common between the two arms will be included in the multiple imputation step. This will mean that for any comparisons including CS4, CS11 and the PMS study, only baseline and Month 9 HFMSE visits will be included in the imputation step and for comparisons including CS4 only, baseline, Month 6 and Month 9 will be included.

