# 6. Efficacy Endpoints

## 6.1. General Analysis Methods for Efficacy Endpoints

## **Multiple imputation (MI)**

Product: Nusinersen	Statistical Analysis Plan
Study: 232SM203	Version: 3.0 Final

The multiple imputation method [Schafer 1997, Schafer 1999] will be used for participants who discontinue for a reason other than death or have a missing efficacy result at the timepoint of interest. This will be performed for CHOP INTEND, HINE Section 2 total score and NF-L. Any imputation on an item level within a scale for CHOP INTEND and HINE section 2 will be performed prior to performing MI.

The imputations will be performed on total scores. All available data will be used i.e., where subjects have missed doses but continued to perform assessments; otherwise, any missing values will be imputed using MI. In a situation where historical data is used as the control group only the visits which are common between the two groups will be utilized. For example, for the CS3B sham control versus higher dose comparison only the Day 64, Day 183 and Day 302 visits will be included in the list of post baseline visits.

In this situation if convergence issues occur then only the Day 64 and Day 183 post baseline visits will be included.

The Markov Chain Monte Carlo (MCMC) method will be used to impute the missing score.

The treatment variable will be coded so that the Higher dose group is the first in the sort order. Prior to the Proc MI step the dataset will be sorted by treatment and then ascending unique subject identifier (USUBJID). The variable list in the model for imputations will include:

- treatment group, disease duration, baseline value for the endpoint, and all available post baseline values
- For NF-L, the log of baseline and post-baseline values will be used in the PROC MI step.

A set of 100 complete imputed datasets will be generated and the relative efficiency parameter will also be checked to determine the acceptability of the imputed results i.e. it should be close to 98% or higher. The seed used for the multiple imputation for CHOP INTEND will be 5846892, for HINE section 2 Motor Milestones will be 8746890 and for NF-L will be 7635789.

If the MI procedure imputes any values outside the expected range for the scale, e.g. from 0 to 64 for CHOP INTEND, then values below 0 will be set to 0 and values above 64 will be set to be 64. For NF-L if any imputed values are  $< \log(LLOQ)$  then set as  $\log(LLOQ/2)$ .

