### Main Analysis

The change from baseline in Plasma NF-L from (ratio to) baseline to Day 183 will be analyzed using the JRT methodology to account for mortality. The ANCOVA model will include covariates for baseline log plasma NF-L, baseline CHOP INTEND total score and disease duration at screening.
 Ranking based on death will be performed as

described earlier for CHOP INTEND. In terms of ranking based on the NF-L, progressively higher ranks will be given to subjects with a greater reduction in NF-L at Day 183.

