# Analysis Methods for HFMSE

The HFMSE is a tool used to assess motor function in children >2 years or older with later-onset SMA. The scale was originally developed with 20 scored activities and was devised for use in children with Type 2 and Type 3 SMA with limited ambulation to give objective information on motor ability and clinical progression. The expanded scale includes an additional module of 13 items developed to alleviate the ceiling effect and allow evaluation of higher functioning and ambulatory SMA patients. Each item is scored 0 (unable), 1 (performs with modification or adaption) or 2 (able) and the total score is calculated by summing the 33 items and ranges from 0 to 66 with higher scores indicating greater motor function. If 6 or fewer items are missing, then these items will be imputed to 0 when summing all 33 items. If greater than 6 items are missing, then the total score will be set to missing.

Baseline is defined as the last non-missing total score prior to the first dose of nusinersen.

In order to further explore the response as measured by HFMSE score a number of thresholds will be evaluated: The proportion of subjects achieving: worsening of >= 4, >= 3, >=2, >=1 points, any worsening, no change (=0 points), any improvement, >=1, >=2, >=3, >=4 points improvement will be presented.

Product: Nusinersen	Statistical Analysis Plan
Study: 232SM203	Version: 1.0

The main analysis is to compare the change from baseline HFMSE score at Day 302 between 50/28 mg Group and 12/12 mg Group using an ANCOVA model with treatment group as a factor and age at screening, baseline Plasma NfL and baseline HFMSE score as covariates. Missing post baseline HFMSE data will be handled using the multiple imputation method.

Several sensitivities will be performed for change from baseline HFMSE:

- The main analysis will be repeated using the PPS.
- The analysis will be performed using a Mixed Effect Model with Repeated Measures (MMRM) with an unstructured covariance matrix, where the treatment group, time (as a categorical variable), treatment by time interaction, and age at screening, baseline Plasma NfL, baseline HFMSE and baseline by time interaction will be included as covariates. No imputation for missing visit data will be performed and the analysis will be performed on the ITT set.
- The missing Day 302 values will be imputed by "last observation carried forward". This will be performed on the ITT set.

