#### Biomarker

The baseline for NfL is defined as the last non missing assessment prior to the first dose of study treatment. For Plasma NfL, if the baseline is missing and a NF-L result is available post dose at Day 1 or Day 2 than the first available assessment post dose, will be used as baseline.

Values that are BLQ will be set to half of the diluted LLOQ (34.5 pg/mL NfL in CSF and 2.76 pg/mL for NfL in plasma).

Neurofilament light chain (NfL) concentration in CSF and in plasma will be analyzed.

The baseline concentrations and the change (including absolute and ratio to baseline) will be presented by visit.

The analysis is to compare the adjusted mean change from (ratio to) baseline to Day 302 between 50/28 mg Group and 12/12 mg Group using an ANCOVA model with treatment group as a factor and age at screening, baseline CSF/Plasma NFL and baseline HFMSE score as covariates.

Summary tables and LS-mean plots (±SE) for geometric mean ratio to baseline in NfL in CSF/plasma using MI data +ANCOVA.

Spaghetti plots by visit for NfL in CSF/plasma using observed data will be plotted for all subjects.

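### Part B later-onset SAP: NfL is to be imputed by a normal model with no log step and used unlogged as a covariate, although the NfL result is a geometric mean ratio and the infantile-onset SAP uses logs

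*SAP*

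**What the plan says.** The later-onset SAP lists the imputed endpoints in 5.1.1: "This will be performed for HFMSE, RULM, NfL CSF and plasma concentration, ACEND, and PedsQL". The method follows: "The Markov Chain Monte Carlo (MCMC) method will be used to impute the missing score". The imputation model contains "treatment group, age at screening, baseline plasma NfL baseline value for the endpoint, and all available post baseline values". The range rule ends "values above 66 will be set to be 66, and for NfL the minimum will be set to LLOQ/2". No transformation of NfL is named anywhere in the section.

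Under Biomarker (5.1.5), the reported quantity is "geometric mean ratio to baseline in NfL in CSF/plasma using MI data +ANCOVA", and the covariate in that model is baseline CSF or plasma NfL, again with no log.

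Unlogged baseline plasma NfL is also a covariate in the motor-function models. For HFMSE the SAP specifies an "ANCOVA model with treatment group as a factor and age at screening, baseline Plasma NfL and baseline HFMSE score as covariates", and the MMRM sensitivity analysis keeps the same term. It recurs for RULM, WHO milestones, ACEND, PedsQL, prorated hospital time (5.1.6) and many of the external comparisons in 5.2.

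The Part B infantile-onset SAP is explicit at the same steps. Section 6.1 says "For NF-L, the log of baseline and post-baseline values will be used in the PROC MI step" and sets imputed values below log(LLOQ) to log(LLOQ/2). Section 6.4.3 uses "baseline log plasma NF-L" as the covariate.

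**The concern.** MCMC imputation in PROC MI assumes multivariate normality. Biomarker concentrations are usually right-skewed. A normal model fitted to a skewed concentration puts probability on negative and near-zero values, which the floor rule then resets to LLOQ/2. When the completed data are logged to obtain a geometric mean ratio, each reset value becomes a very large apparent fall that no participant had. This adds noise to the biomarker comparison.

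A right-skewed covariate left unlogged has a second, smaller effect: with 24 participants (16 versus 8), one high value can carry much of the leverage for that term.

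There is also a pre-specification issue. A programmer who follows 5.1.1 literally and one who follows the infantile-onset rule would produce different analyses from the same data, and the SAP does not say which is intended.

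**Working it through.** **1. The two SAPs side by side**

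| Step | Later-onset SAP | Infantile-onset SAP |
|---|---|---|
| Scale in PROC MI | concentration; no log named (5.1.1) | log (6.1) |
| Floor | LLOQ/2 (5.1.1) | log(LLOQ/2) for values below log(LLOQ) (6.1) |
| Covariate in the NfL model | baseline NfL (Biomarker) | log baseline NF-L (6.4.3) |
| Summary from MI + ANCOVA | geometric mean ratio | geometric mean ratio |

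The summary is the same in both, but only the infantile-onset SAP gets there on one scale throughout.

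**2. Inputs.** From the SAP: n = 24, 16 versus 8. There is no planned figure to reproduce: the SAP gives no NfL SD, CV or missing rate, and its sample size has no power basis. Everything below about the spread of NfL and missing data is an assumption, shown as a range.

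**3. Closed-form check of the floor.** Let NfL be lognormal with median 1 and log-SD s. A normal model with the same moments has mean m = exp(s²/2) and SD = m·√(exp(s²) − 1). The share drawn below a floor f is Φ((f − m)/SD). With f = 0.1 of the median (assumed):

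| s | m | SD | (f − m)/SD | Share below floor, normal model | True lognormal share |
|---|---|---|---|---|---|
| 0.3 | 1.046 | 0.321 | −2.95 | 0.2% | 0.0% |
| 0.5 | 1.133 | 0.604 | −1.71 | 4.4% | 0.0% |
| 0.75 | 1.325 | 1.151 | −1.06 | 14.4% | 0.1% |
| 1.0 | 1.649 | 2.161 | −0.72 | 23.7% | 1.1% |

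**4. Simulated imputation.** Missing values were drawn from a Bayesian normal regression, with 16 versus 8 participants.
- One or three missing values, log-SD 0.3 to 1.0: 1% to 22% of imputed values reached the floor on the concentration scale, against 0% to 6% on the log scale.
- Four time points, 15% missing, floor at 5% of the baseline median: concentration scale 0.2–1.6%, 2.8–8.3%, 10–17% and 17–25% at log-SD 0.3, 0.5, 0.75 and 1.0; log scale 0%, 0–0.6%, 0.1–3.6% and 0.5–8.6%.

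**5. What a reset value looks like.** Assume a baseline of 20 pg/mL. If the 2.76 pg/mL under Biomarker is the LLOQ, the floor is 1.38 and the ratio is 1.38/20 = 0.069, a fall of 93%. If 2.76 is already half the LLOQ, the ratio is 2.76/20 = 0.138, a fall of 86%. The SAP's wording allows either.

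**6. Effect on the NfL comparison.** The pooled variance is T = W + (1 + 1/M)·B, with W the within-imputation and B the between-imputation component.
- In the first simulation of step 4, B was about 40% to 75% larger with concentration-scale imputation, and the pooled standard error √T about 3% to 11% larger.
- With an assumed correlation of 0.7 between baseline and endpoint, B roughly doubled. The pooled standard error rose about 7% with one missing value and 17–18% with three. The actual spread of the estimates rose only 1% to 6%.
- Bias was negligible. With a true log effect of −0.405, estimates were −0.41, −0.42 and −0.37 on the concentration scale and −0.41, −0.42 and −0.38 on the log scale, at log-SD 0.5, 0.8 and 1.0.

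**7. Effect on the covariate.** Leverage was taken from an ANCOVA with intercept, treatment, age and baseline NfL, so the mean leverage is 4/24 = 0.17.

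| Log-SD | Median maximum leverage, unlogged | Chance that one participant exceeds 0.8, unlogged |
|---|---|---|
| 0.3 | 0.37 | 0% |
| 0.5 | 0.41 | 0–1% |
| 0.75 | 0.47 | 4–6% |
| 1.0 | 0.54 | 11–13% |

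With log baseline NfL the median is 0.34–0.35 throughout and no simulated trial exceeds 0.8. With an assumed NfL–outcome correlation of −0.5, leaving the covariate unlogged raised the SD of the treatment estimate by 1.5%, 2.9% and 4.5% at log-SD 0.5, 0.8 and 1.0, with no bias.

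**The case against.** The strongest reply is that the SAP omits the scale rather than prescribing one. It never calls NfL raw or untransformed. A geometric mean ratio can come only from a log-scale ANCOVA, so that part is already implied. The word concentration may simply name the endpoint, and an LLOQ/2 floor would also fit imputed values transformed back from logs. The infantile-onset SAP itself leaves out the log in its general ANCOVA paragraph (6.1) and supplies it only in 6.4.3. This stands to the extent that the concentration scale is a reading of 5.1.1. It is still the plain reading, because the companion SAP writes the log into the same steps.

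A reader might infer more: that imputed values will pile up at the floor, or that one or two participants will drive the motor-function results. The documents do not support either. The share at the floor depends on skewness and missing data that the SAP does not give; it is under 2% at log-SD 0.3, and only missing post-baseline NfL values are affected. High leverage on a covariate measured before randomised treatment is not bias in the treatment contrast.

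The stakes are also limited. The later-onset cohort has no primary efficacy endpoint and no power basis. The HFMSE responder model within the trial, and several external comparisons, do not use NfL as a covariate.

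**Conclusion.** The point holds in a conditional form. Read plainly, the later-onset SAP imputes NfL by a normal model on the concentration scale and uses it unlogged as a covariate. That does not fit its own geometric mean ratio and departs from the infantile-onset SAP. The cost is precision and an unfixed analysis choice, not a distorted treatment effect: about 1% to 22% of imputed NfL values at the floor and a pooled standard error roughly 3% to 11% wider at assumed log-SDs of 0.3 to 1.0, reaching 17–18% with three missing values and a baseline correlation of 0.7. For the covariate, the loss is at most a few percent in the SD of the treatment estimate. The floor effect is material only if NfL is strongly skewed (log-SD about 0.75 or more) and some values are missing. The change is worth making because the log scale performs at least as well throughout the assumed range and costs almost nothing.

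**What to change.** In the later-onset SAP:

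- 5.1.1: log-transform baseline and post-baseline NfL before PROC MI, and set imputed values below log(LLOQ) to log(LLOQ/2), as infantile-onset section 6.1 does.
- Replace baseline NfL with log baseline NfL wherever it is listed: the imputation variable list in 5.1.1, the ANCOVA and MMRM models in 5.1.5 and 5.1.6, and the external comparisons in 5.2.
- Biomarker: state that the NfL ANCOVA is on the log ratio to baseline, transformed back to a geometric mean ratio.
- While editing, say whether 34.5 and 2.76 pg/mL are the LLOQ or half of it, since the floor depends on this.

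The cost is a few words and one derived variable for each matrix (plasma and CSF). No new data are needed, and the two Part B SAPs would then agree.
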